2.0 Rationale and Specific Aims

We hypothesize that patients with T1DM who have reduced pancreatic volume will have improved glycemic responsiveness, reduced hypoglycemia, and improved symptoms of pancreatic exocrine insufficiency (PEI) when treated with pancreatic enzyme replacement. To test our hypotheses, we will employ a double-blinded crossover study. This study will be a pilot study to gather preliminary information on potential effect size in preparation for a larger study if supported by these results. The study will enroll approximately 15 adult subjects with T1D who will receive both pancreatic enzyme replacement (Creon) or placebo each for 7 days in a random order. The effect of the intervention will be monitored by continuous glucose monitoring, diet recording, capsule counts, a mixed-meal tolerance test, and a survey to assess symptoms of PEI. This study design will allow for estimation of the effect of pancreatic enzyme replacement on the measured parameters.

Aim 1 will provide preliminary estimates of the effect of enzyme replacement on glucose responsiveness, variability, and hypoglycemia. We will download and analyze CGM data to determine changes occurring in measures of glycemic variability and in the duration and severity of hypoglycemia. Data will be divided into 4 7-day blocks including a run-in period, treatment A, a wash out period, and treatment B. Participants will track their meal composition, report daily exercise duration, and a capsule count will be obtained. At the end of treatment A and treatment B, participants will undergo a mixed meal tolerance test (MMTT) in which glucose, C-peptide, GLP-1, GIP, and glucagon will be measured at defined timepoints.

Aim 2 will provide an initial assessment of the effect of enzyme replacement on symptoms of pancreatic exocrine insufficiency in T1D. We will use the PEI-Q to quantitate symptoms of PEI and their relative change during enzyme replacement at each of the 4 intervals. The frequency and degree of PEI symptoms has not been objectively measured in T1D patients previously.

We will obtain information on the adherence to the intervention and will obtain initial information on median and standard deviation for measured variables that will inform future studies. We will perform a paired t-test to provide an initial assessment of outcomes between groups.

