10.0 Statistical Considerations

10.1 Recruitment

We have targeted an accrual of 15 participants in this pilot study. We will estimate the effect size and variance of the intervention on glycemic variability and symptoms. We will also ascertain the intra-individual variation from comparison between our two non-treatment intervals (run-in and wash-out periods) which will set a lower bound on measurable effects. To estimate the pilot study's optimum accrual, we utilized the method of Whitehead et al. which proposes stepped increases in sample size based on the anticipated standard difference, d, between interventions^{1,2}. We defined the minimum important difference (MID) in low blood glucose index, a measure of low blood glucose from CGM data) between enzyme replacement and placebo interventions as 1 (difference in values of 3 for more variable and 2 for less variable as reflected in clinical experience) and estimated a pooled SD of 1.29 based on our review of CGM data from other studies. If d=MID/SDpooled=1/1.29=0.77, a sample size of 15 participants per arm will optimize future sample size calculations for a definitive study.

10.2 Statistical Analysis Statistical analysis will be performed using a paired samples t-test to compare differences between the two groups.

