Pancreatic enzyme replacement and glucose regulation in Type 1 diabetes

NCT05266963

Statistical Analysis Plan

12/4/2023

Statistical Analysis Plan

NCT05266963 - Pancreatic Enzyme Replacement and Glucose Regulation in Type 1 Diabetes (CREON)

Background

In T1D, there is significant reduction in pancreas volume. The biological impact of this is not known. Because islet cells make up a small fraction of pancreas size, the major reduction in volume is due to loss of exocrine tissue. Since patient with T1D have substantial loss of exocrine tissue and pancreatic enzymes support glucoe regulation and pancreas function, this study tests the hypothesis that pancreatic enzyme replacement will improve C-peptide secretion to regulate glucose excursions and/or will improve symptoms of pancreatic enzorine insufficiency. This document provides additional description of the analysis plan and complements the protocol document where study details are provided.

Primary objective

Aim 1: To assess impact of pancreas enzyme replacement on C-peptide auc in subjects with T1D and reduced pancreas volume

Aim 2: To assess the impact of pancreas enzyme replacement on symptoms of pancreatic exocrine insufficiency (PEI) in T1D.

Secondary Objectives

Secondary assessments will be made to explore mechanisms of effect if the primary outcome is met. These could include analysis of CGM data, measure of circulating hormones and cytokines, assessment of dietary intake.

Trial Design

The study is a single center, double-blinded randomized cross over design in which subjects receive Creon or placebo each for 1 week with a 1 week washout period between.

Eligibility

Inclusion Criteria	Exclusion Criteria
 Diagnosed with T1DM for at least	 History of celiac disease or
12 months Age over 18 Total daily dose of insulin greater	inflammatory bowel disease Unwilling to temporarily discontinue
than 0.6u/kg/day	use of medication or supplements

 Current use of a CGM 	other than insulin to control blood
 Current use of smart phone 	glucose
 Able to read and speak English 	 Pregnant or breast feeding
 Willingness and ability to download and provide CGM and pump (if applicable) data Reduction of pancreas volume (<0.6mL/kg BW) 	 Following a restrictive diet (such as very low carb diet) History of major bowel or bariatric surgery

Treatment

Participants will continue their standard care for diabetes with calculation and adjustment of doses per their primary endocrinologists.

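### The SAP makes CGM analysis optional and dependent on an undefined primary success, although the protocol promises CGM estimates outright and sizes the pilot on a CGM measure

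*SAP*

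**What the plan says.** **Protocol (version 6, 04DEC2023).** Section 2.0 states: "Aim 1 will provide preliminary estimates of the effect of enzyme replacement on glucose responsiveness, variability, and hypoglycemia". It continues: "We will download and analyze CGM data to determine changes occurring in measures of glycemic variability and in the duration and severity of hypoglycemia". The data are to be split into four 7-day blocks. Section 10.1 adds: "We will estimate the effect size and variance of the intervention on glycemic variability and symptoms", and "We will also ascertain the intra-individual variation from comparison between our two non-treatment intervals", meaning run-in and wash-out. The accrual target rests on a CGM measure: "We defined the minimum important difference (MID) in low blood glucose index", set at 1, with a pooled SD of 1.29. None of these statements depends on another result.

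**SAP (12/4/2023).** The primary objectives are "Aim 1: To assess impact of pancreas enzyme replacement on C-peptide auc in subjects with T1D and reduced pancreas volume" and "Aim 2: To assess the impact of pancreas enzyme replacement on symptoms of pancreatic exocrine insufficiency (PEI) in T1D". Primary Outcome Analysis gives a Wilcoxon matched-pairs comparison for C-peptide AUC and a t-test for PEI-Q severity. CGM appears under Secondary Objectives: "Secondary assessments will be made to explore mechanisms of effect if the primary outcome is met. These could include analysis of CGM data". Exploratory Analysis allows further work if the primary endpoint is met or if a journal or editor asks for it. CGM downloads are collected regardless, but the SAP names no CGM endpoint, no LBGI analysis and no run-in versus wash-out comparison. Its Background section describes it as a complement to the protocol.

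**The concern.** An analyst cannot follow both documents if the primary result is not favourable: the protocol requires the CGM estimates and the SAP then gives no instruction to produce them. Even when the condition is satisfied, the SAP says only that CGM could be among the assessments.

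The condition is also undefined. The SAP speaks of one primary outcome but lists two measures, each with its own test. It does not say whether C-peptide alone, either measure or both must succeed, and it states no significance level. Whether CGM is analysed could therefore be settled after the primary results are known.

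Protocol section 2.0 describes a pilot meant to gather preliminary effect-size information for a larger study. Making secondary tests conditional on the primary protects confirmatory claims. Here it protects nothing and can withhold the inputs that the next trial needs. If the C-peptide or PEI-Q differences are correlated with the CGM differences, reporting CGM only after a significant primary would also bias the glycaemic estimate. The documents give neither the sign nor the size of that correlation, so I put no figure on the bias.

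**Working it through.** **1. The plan's own figure.** Section 10.1 gives d = MID/SD = 1/1.29 = 0.775, printed as 0.77, so the ratio reproduces apart from truncation. The step from there to 15 per arm uses a stepped rule from a cited source. The documents do not give the steps, so 15 cannot be reproduced from them. What matters here is that the sizing variable is LBGI, which the SAP never mentions.

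**2. How often the condition would leave CGM unanalysed.** From the documents: 15 participants, Wilcoxon for C-peptide and a matched t-test for PEI-Q. Assumed, because the documents are silent: all 15 complete, two-sided 5% per measure, normal paired differences, and independent primaries unless stated. Effects are in SDs of the paired differences.

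Exact Wilcoxon signed-rank test at n = 15: reject if min(W+, W−) ≤ 25, true size 0.0479. Power, with 400,000 simulated trials per setting:

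| True effect on both | Wilcoxon (p1) | Paired t (p2) |
|--|--|--|
| 0.3 SD | 0.181 | 0.192 |
| 0.5 SD | 0.417 | 0.438 |
| 0.8 SD | 0.801 | 0.821 |

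The probability that the condition fails is:

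- C-peptide must succeed: 1 − p1
- either suffices: (1 − p1)(1 − p2)
- both needed: 1 − p1·p2

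At 0.5 SD these are 1 − 0.417 = 0.583; 0.583 × 0.562 = 0.328; and 1 − 0.417 × 0.438 = 0.817 (0.818 by simulation). All settings:

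| True effects | C-peptide alone | Either | Both |
|--|--|--|--|
| None on either | 95% | 90% | over 99% |
| 0.3 SD on both | 82% | 66% | 97% |
| 0.5 SD on both | 58% | 33% | 82% |
| 0.5 SD on both, primaries correlated 0.5 | 58% | 40% | 74% |
| 0.8 SD on both | 20% | 4% | 34% |
| None on C-peptide, 0.5 SD on PEI-Q | 95% | 54% | 98% |

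These are the chances that the condition fails. When it holds, the CGM analysis is still only optional.

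**3. What unconditional reporting would give.** With 15 pairs, the 95% CI half-width for a mean paired difference is t(0.975, 14)/√15 = 2.145/3.873 = 0.55 SD of the differences. The 95% CI for that SD runs from 0.73 to 1.58 times its estimate. In LBGI units, suppose 1.29 is the SD in each period and the between-period correlation r lies between 0 and 0.7 (assumed). The SD of the differences is 1.29 × √(2(1 − r)), or 1.82 down to 1.00, and the half-width is 1.01 down to 0.55, against an MID of 1. The estimates are imprecise but usable for planning.

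**The case against.** The strongest reply is that the SAP complements the protocol and does not replace it. On that reading, the conditional sentence covers only mechanistic exploration, it says *if* and not *only if*, and the descriptive CGM estimates still stand under the protocol. The reading is possible, but the SAP does not state it. The SAP attaches an explicit condition to the same CGM data and specifies no unconditional CGM analysis, so the two texts still have to be reconciled.

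Second, the SAP Background joins the C-peptide and symptom hypotheses with an and/or, which favours the *either* column. That is fair, and the *both* column should carry less weight. But it defines neither success nor a significance level, and under *either* the condition still fails in 33% of trials at 0.5 SD and in 90% with no effect.

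Third, the effect sizes, alpha and correlation are not in the documents. That is true: the percentages are illustrations, and the conflict is textual and does not need them.

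Fourth, CGM data are collected regardless, so nothing is lost for good and the primary comparisons are untouched. This makes the fault cheap to mend. It does not ensure that the estimates are produced, or that they are reported independently of the primary results.

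**Conclusion.** The concern holds. Two documents of the same date conflict on whether the pilot's glycaemic estimates will be produced, and the SAP has no analysis of the variable on which the trial was sized. C-peptide is itself one of the MMTT measures in protocol Aim 1, so that part of the aim is still analysed; it is the CGM part that has become optional. The two primary measures are named, but which of them must succeed, and by what criterion, is not.

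Under the assumptions listed above, the chance that the condition fails ranges from 4% (0.8 SD on both, either suffices) to over 99% (no effect, both needed). Because success is undefined, the SAP does not say which column applies. This should be corrected before the data are analysed.

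**What to change.** 1. In the SAP, remove the primary-success condition for CGM. State that the Creon minus placebo paired differences in LBGI, time below 70 mg/dL and glucose SD will be reported with their SD and 95% CI, labelled as estimation, whatever the C-peptide or PEI-Q result. LBGI is the essential one; it can be derived, since protocol section 6.1.4.2 collects all glucose values.
2. Use all participants with CGM data in both treatment weeks. Say how this set relates to the SAP's restriction to those completing both arms and to its possible adherence exclusions.
3. Add the run-in versus wash-out within-person variation promised in protocol section 10.1.
4. Word Aim 1 the same way in both documents, covering the CGM measures and MMTT C-peptide.
5. If any other assessment stays conditional, state which primary opens it and at what alpha. The circulating hormones need a decision here: the SAP puts them under the same condition, while protocol Aim 1 lists GLP-1, GIP and glucagon among the MMTT measurements.

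The cost is SAP wording and a few analyses of data already collected, with no new participants or visits.
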